8.4.3 Safety Analyses

For safety analyses, separate summaries taking into account length of treatment (28 or 90 days) and randomization phase (randomization prior to or after DMC safety interim analysis decision) will be provided.

The proportion of subjects with the composite of major bleeding and CRNM bleeding, and additional bleeding endpoints such as all bleeding events (including major bleeding, clinically relevant non-major bleeding and minor bleeding) and intracranial hemorrhage during the treatment period will be summarized by treatment. Point estimates and 95% CIs for event rates of each of above safety endpoints will be presented by treatment, together with point estimates and 95% CIs for the difference of event rates between each BMS-986141 arm and placebo. A single variable based on study change points (length of treatment [28 or 90 days] and randomization phase [randomized prior to or after DMC safety interim analysis decision]) will be included as a stratum in the calculation of the CIs.

The number and percent of subjects with at least one adverse event will be summarized for each treatment group, including summaries of AEs, SAEs, AEs leading to discontinuation, and AEs of special interest. Summaries will include the number of subjects with events by specified system organ classes and preferred terms. All endpoint events reported by the investigator as AEs (serious or non-serious) will be reported in the safety analyses, regardless of whether the event was confirmed by adjudication. The number and percent of subjects with marked laboratory abnormalities will be similarly presented.

Values and changes from baseline at each scheduled time point for clinical laboratory parameters, vital signs, and ECG will be summarized by treatment group using descriptive statistics.

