2.2 Treatment Assignment

At the screening visit each subject will be assigned a unique sequential subject number by the Interactive Voice Response System (IVRS). The subject number will consist of 5 digits which are assigned sequentially (00001, 00002, 00003, etc.) by the IVRS. This number will be used for

identification throughout the study and will not be used for any other participant. Screening of subjects with lacunar infarcts will be capped at approximately 20%.

In addition to the two Parts of the study noted above, which are related to treatment duration, the study also consists of two phases, each with a slightly different method of assigning study treatment. In Phase A, subjects will be randomized 1:1:1 using IVRS to one of two doses of BMS-986141 (0.8 mg or 4.8 mg) or placebo. In Phase B, subjects will be randomized 1:1:1:1 via IVRS to one of three doses of BMS-986141 (0.8 mg, 4.8 mg, or 8 mg) or placebo. The transition from Phase A to Phase B of the study will only occur after an Independent Data Monitoring Committee (DMC) has reviewed data from the first 10% of the planned subjects (approximately 132 subjects with 28 days of data). As of the time of the writing of this SAP, the decision to move from Part 1 to Part 2 of the study has been made. Some sites will continue to enroll subjects in to Part 1 of the study until Part 2 can be fully implemented. As a result, there will be no subjects randomized in Phase B during Part 1 of the study.

Randomization schedules will be generated by BMS and kept by the IVRS vendor. All subjects will receive open-label ASA at a dose from 75 to 162 mg per day beginning at a time consistent with local standards of care for patients with AIS or TIA. As mentioned in [section 2.1](#), the planned study dosing duration is 28 days for Part 1 of the study and 90 days for Part 2 of the study.

At all study visits when study drug is dispensed, each subject will be assigned a container number by the IVRS. Container numbers will be assigned non-sequentially and will correspond to the numbers printed on the packages and bottles containing study drug, and will be recorded on the appropriate eCRF. The IVRS will be available 24 hours per day, 7 days a week.

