2.4 Protocol Amendments

A protocol revision was formally issued on 07-July-2016, incorporating several design changes into the study. Most notably, the original planned high dose of BMS-986141 was reduced from 16 mg to 8 mg, and this arm of the study is to be closed off until the Data Monitoring Committee is able to evaluate sufficient safety data from the 2 lower dose groups (0.8 mg and 4.8 mg). To that effect, the randomization scheme was updated to keep the 8mg arm closed until the DMC convened. Pending the outcome of the DMC meeting, the 8mg arm would open and randomization would proceed in a 1:1:1:1 fashion from there forward to one of the three BMS-986141 doses or placebo (see [Table 5-1](#)).

Additional updates were made to clarify various aspects of the study and can be found in the protocol revision. No further updates had a significant impact to the statistical methods planned for this study.

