5 SAMPLE SIZE AND POWER

The primary efficacy endpoint of the study is the incidence of a composite of symptomatic ischemic stroke by Day 28 and unrecognized brain infarction at Day 28. Sample size calculations were performed for detecting a dose-response effect with the MCP-MOD methodology using simulations with the DoseFinding package in R⁴. Simulations of 1000 clinical trials were performed, assuming a true incidence for placebo of 14%, a maximum relative risk reduction of 30% for BMS-986141 8 mg relative to placebo, and relative reductions of 75% and 90% of the maximum for the 0.8 and 4.8 mg doses, respectively. Candidate models included an Emax model and a logistic model.

Initially, randomization will be limited to the two lower doses of BMS-986141 (0.8 mg or 4.8 mg) or placebo in a 1:1:1 ratio until after the DMC review of safety and laboratory data from the Day 28 study visit for at least 10% of planned total subjects (approximately 132 subjects). If the DMC recommends proceeding to inclusion of the highest dose (8 mg), subsequent randomization will be in a 1:1:1:1 ratio. Based on the staggered randomization as shown in in the table below and the assumptions above, the study will have at least 80% power to demonstrate a dose-response relationship, using a 1-sided type I error rate of 15%. A total sample size of 1312 randomized subjects accounts for about 5% of subjects without post-randomization data.

Table 5-1: Randomization Targets

	Placebo	0.8 mg	4.8 mg	8 mg
Prior to interim safety review by the DMC: 132 subjects (1:1:1 randomization ratio)	44	44	44	0
Additional subjects randomized while interim safety reports are being generated and reviewed by the DMC (not included in the DMC safety interim analysis): 100	34	33	33	0

Table 5-1: Randomization Targets

	Placebo	0.8 mg	4.8 mg	8 mg
subjects (1:1:1 randomization ratio)				
After interim safety review by DMC: 1081 subjects	270	270	270	270
Total: 1312 subjects	348	347	347	270

Note: Numbers shown for each treatment group are estimates based on randomization ratio. Actual numbers could be slightly different based on randomization block size and rate of enrollment.

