7.1.1 General Methods for Study Periods

Given the different planned study treatment durations between Part 1 (treatment duration of 28 days) and Part 2 (treatment duration 90 days) and time at which randomization will be extended to include the high dose of BMS-986141 (8 mg) following review of safety data by the DMC, select summaries will be tabulated by the following three applicable study time periods with respect to study part and study phase:

- Part 1, Phase A (1A)
- Part 2, Phase A (2A)
- Part 2, Phase B (2B)

Summaries will also be tabulated for Part 2 overall, to include data from all subjects with a planned treatment duration of 90 days. The following summaries will be tabulated as indicated above.

- Demographics
- Baseline characteristics
- Relevant protocol deviations
- Disposition
- Concomitant medications, including CYP3A4 inhibitor use
- Study drug exposure and compliance
- Bleeding events
- Adverse events, including overall AEs, SAEs, AEs leading to discontinuation, related AEs, and deaths
- Abnormal laboratory results, including renal biomarkers
- Abnormal ECG results
- Out of range vital signs

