7.1.2 General Methods for Efficacy Analyses

Generalized Multiple Comparison Modelling (gMCP-Mod)

To demonstrate the dose-response relationship between BMS-986141 treatment (including placebo) and the primary endpoint, the primary analysis will be based on a generalized Multiple Comparisons and Modeling (gMCP-Mod) analysis⁵⁶. This analysis tests for a dose-response relationship, allowing for uncertainty in the dose-response relationship through inclusion of contrasts from multiple pre-specified candidate models to assess dose-response. If a dose-response relationship exists, then fitted estimates for the incidence of the primary endpoint will be calculated in each of the treatment groups using the selected dose-response models.

The gMCP-Mod procedure extends the MCP-Mod methodology to non-continuous endpoints. This is accomplished by decoupling the dose-response model from the expected response through the use of an ANOVA style parameterization of the dose-response parameter. For the binary endpoint used in this study, a logistic regression of the event proportion at each dose level will be used, following adjustment for study time period (1A, 2A, 2B) via the inclusion of an additive covariate. After this first step, the mean parameter estimates from the logistic model and the corresponding covariance matrix, both of which are on the logit scale, will then be used during the rest of the gMCP-Mod procedure. Point estimates from the selected models will be displayed on the proportion scale in all statistical outputs.

Candidate Models and Multiple Testing Procedure

There are two candidate models that will be considered for the primary analysis. These are an Emax model and a logistic model, where dose-response will be tested using dose levels of 0 (placebo), 1, 2, and 2.3 (corresponding to 0.8 mg, 4.8 mg, and 8 mg)⁷.

The MCP-Mod procedure requires certain parameter estimates be pre-specified for the candidate models based on available information in order to derive optimum contrast coefficients for testing the null hypothesis: that a dose-response does not exist in any of the candidate models. It

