7.2.2 Relevant Protocol Deviations

Relevant deviations from the study protocol will be documented and accounted for in presenting the data summaries, listings and descriptive statistical analyses. Any changes from planned protocol-specified analyses will be defined in the SAP and reported in the CSR. The relevant protocol deviations are described in the table below.

Table 7.2.2-1: List of Relevant Protocol Deviations

Number	RPD Criteria
1	Subject randomized but not dosed
2	Error in treatment assignment (resulting in a subject receiving a treatment other than that assigned by the IVRS) during the first 28-day interval
3	Poor treatment compliance for either BMS-986141 or ASA (compliance less than 80% or more than 120%) during first 28-day interval
4	Randomized subjects with history of atrial fibrillation (AF) other than transient AF related to cardiac surgery at enrollment (per Exclusion Criteria 1a from the protocol)
5	Randomized subjects with unrecognized or misdiagnosed intracranial hemorrhage (ICH) as determined by the central reader based on the baseline study specific MRI (presence of type 1 or 2 parenchymal hematoma)
6	Randomized subjects who took no dose of ASA or dose of ASA not within limits designated by the protocol for ≥ 5 consecutive days in the first 28 days of the treatment period
7	Randomized subjects who took oral anticoagulants or prohibited antiplatelet therapy, other than study medication, for > 2 consecutive days during the first 28days of the treatment period
8	Randomized subjects that were treated with a strong CYP3A4 inhibitor for > 5 days during the first 28 days of the treatment period ^a

a: CYP3A4 inhibitors will be defined in a separate file maintained by the study team and will be classified as weak, moderate, or strong.

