All AEs will be coded and grouped into Preferred Terms (PT) by System Organ Class (SOC), using the most current available version of Medical Dictionary for Regulatory Activities (MedDRA). Summaries of AEs will use the version of MedDRA that is current at the time of database lock. All recorded adverse events will be listed and tabulated by SOC, PT, treatment and overall. Values for ECGs, vital signs, and clinical laboratory test results will be summarized by treatment. Abnormal results for ECG, vital signs and clinical laboratory tests that fall outside the pre-specified criteria will also be listed and summarized. In addition, ECG readings will be evaluated by the Investigator and abnormalities, if present, will be listed.

7.6.1 *Major Bleeding and Clinically Relevant Non-Major Bleeding*

The proportion of subjects with adjudicated bleeding events which occur on or after the first dose of study treatment and within 4 days after the last dose of study treatment will be summarized by treatment. Point estimates and 95% exact CIs for event rates of each of the below bleeding endpoints will be presented by treatment, together with point estimates and 95% exact CIs for the difference of event rates between each BMS-986141 arm and placebo. The following bleeding endpoints will be analyzed using these methods.

- The proportion of subjects with the composite of adjudicated major bleeding and CRNM bleeding
- The proportion of subjects with all reported bleeding
- The proportion of subjects with intracranial hemorrhage

All adjudicated bleeding events will be listed. In addition, the proportion of subjects with confirmed major bleeding or clinically relevant non-major bleeding events occurring during the treatment period will be summarized by treatment group for each of the following factors.

- Stroke severity (based on National Institutes of Health Stroke Scale NIHSS) at study entry
 - NIHSS Score of 0 (No stroke symptoms)
 - NIHSS Score of 1-4 (Minor stroke)
 - NIHSS Score of 5-15 (Moderate stroke)
- Lacunar infarct at study entry
 - Yes
 - No

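### SAP 7.6.1 drops, without declaring it, the protocol's treatment-length and randomization-phase stratum from the bleeding CIs, which leaves the pooled 8 mg versus placebo contrast confounded

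*SAP*

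**What the plan says.** Protocol 8.4.3, repeated in the synopsis, asks for bleeding rates by arm and for arm-minus-placebo differences with 95% CIs. It adds that the single study-change-point variable (28 or 90 days of treatment; randomized before or after the DMC decision) "will be included as a stratum in the calculation of the CIs". The protocol's change list shows that Amendment 06 introduced this stratum.

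SAP 7.6.1 covers the same endpoints: major plus CRNM bleeding, all bleeding, and intracranial hemorrhage. It counts events from the first dose to 4 days after the last dose and summarizes them by treatment, "together with point estimates and 95% exact CIs for the difference of event rates between each BMS-986141 arm and placebo". It mentions no stratum.

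SAP 7.2.2 states: "Any changes from planned protocol-specified analyses will be defined in the SAP and reported in the CSR". No change is defined for bleeding. SAP 2.4, after describing the new top dose and the staggered randomization of Amendment 06, says: "No further updates had a significant impact to the statistical methods planned for this study".

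For efficacy the SAP does carry the adjustment over. In SAP 7.1.2 the logistic regression is fitted "following adjustment for study time period (1A, 2A, 2B) via the inclusion of an additive covariate".

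**The concern.** The three active arms do not share one period structure. SAP 2.2 says that "there will be no subjects randomized in Phase B during Part 1 of the study". The 8 mg arm opens only in Phase B, so every 8 mg subject falls in period 2B with 90 planned days of treatment. Placebo subjects are spread over 1A (28 days), 2A (90 days) and 2B (90 days).

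A pooled 8 mg minus placebo difference therefore compares an arm observed entirely on the longer schedule with one observed partly on the shorter schedule and partly in an earlier calendar period. The 0.8 and 4.8 mg arms have almost the same period mix as placebo, so their contrasts are unaffected. The distortion falls on the primary safety comparison for the top dose, the dose held back for safety review, and on the apparent step in bleeding from 4.8 to 8 mg. Longer exposure alone makes an inert 8 mg dose look worse than placebo. It would not hide a real signal. A change in bleeding rates over calendar time could push the estimate either way.

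**Working it through.** **Planned numbers (SAP Table 5-1)**

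| Stage | Placebo | 0.8 mg | 4.8 mg | 8 mg |
|---|---|---|---|---|
| Before DMC review | 44 | 44 | 44 | 0 |
| During DMC review | 34 | 33 | 33 | 0 |
| After DMC review | 270 | 270 | 270 | 270 |
| Total | 348 | 347 | 347 | 270 |

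The arm totals and the overall 1312 reproduce. The Phase A share is (44 + 34)/348 = 22.4% for placebo, 77/347 = 22.2% for each lower dose, and 0/270 for 8 mg.

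**Bleeding window.** The last dose plus 4 days gives 28 + 4 = 32 days in Part 1 and 90 + 4 = 94 days in Part 2.

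**Assumptions, because the documents are silent.** There is no drug effect, the hazard is constant, and R is the 94-day bleeding risk. Of the 78 Phase A placebo subjects, n1 are in Part 1. The case n1 = 78 is only an upper bound, because SAP 7.1.1 lists a period 2A.

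**Formulas**

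- F(32) = 1 − (1 − R)^(32/94)
- Pooled placebo risk = [n1 × F(32) + (348 − n1) × R]/348
- Spurious excess at 8 mg = R − pooled placebo risk

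**Central case, R = 5% and n1 = 39.** F(32) = 1.73%. Pooled placebo risk = (39 × 1.73% + 309 × 5%)/348 = 4.634%. The excess is 0.366 points, with risk ratio 5/4.634 = 1.079. In 270 subjects this is about one event.

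**Range**

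| Case | Excess (points) | Risk ratio |
|---|---|---|
| R = 2%, n1 = 39 | 0.147 | 1.08 |
| R = 8%, n1 = 39 | 0.583 | 1.08 |
| R = 5%, n1 = 20 | 0.188 | 1.04 |
| R = 5%, n1 = 39, 50% of bleeds within 32 days | 0.280 | 1.06 |
| R = 5%, n1 = 39, 60% of bleeds within 32 days | 0.224 | 1.05 |
| R = 5%, n1 = 39, 10% stop treatment by Day 90 | 0.342 | 1.08 |
| R = 5%, n1 = 39, 30% stop treatment by Day 90 | 0.291 | 1.07 |
| R = 5%, n1 = 78 (upper bound) | 0.733 | 1.17 |

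**Against sampling error.** In the central case the standard error of the pooled difference, using each arm's own expected risk, is 1.74 points. Bias/SE = 0.366/1.74 = 0.21, and nominal 95% coverage falls to about 94.5%.

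**Calendar drift alone.** If the Phase A rate is r times the Phase B rate p, the bias is (78/348) × p × (1 − r). With p = 6% this is +0.27 points at r = 0.8 and −0.67 points at r = 1.5.

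**Cost of stratifying.** A Mantel-Haenszel stratum weight is zero where one arm is empty, so the 8 mg contrast reduces to 2B, 270 against 270. The SE ratio is √[(1/270 + 1/270)/(1/270 + 1/348)] = 1.061. At a 5% risk in both arms, that is 1.88 against 1.77 points.

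**The case against.** The strongest reply is that the SAP already plans most of what is needed. SAP 7.1.1 lists bleeding among the summaries tabulated by 1A, 2A and 2B, and SAP 7.6 repeats by-period frequency summaries. Since the stratified 8 mg contrast is simply 2B against 2B, its counts will be on the page. Table detail is left to a Data Presentation Plan that we do not have. This is real mitigation. But neither section says that those tables carry differences or intervals, so the interval the protocol requires is still not specified.

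The second reply is that the bias is smaller than the price of removing it. In the central case the root mean squared error is √(1.74² + 0.366²) = 1.78 points for the crude difference, against 1.88 stratified. With all 78 in Part 1 it is 1.86 against 1.88, and only at 8% risk with all 78 does the crude estimate do worse (2.43 against 2.33). This arithmetic is right and limits the severity. It leaves out calendar drift, however, and it does not justify replacing a prespecified concurrent comparison without saying so.

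It is also fair that the documents contain no evidence of drift, that no dose-selection rule is tied to the final bleeding contrasts, that these are estimates and not tests, and that the protocol mentions the stratum only for the CIs. On the last point, a stratified interval needs a matching stratified estimate, and SAP 7.6.1 supplies neither.

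**Conclusion.** The concern holds and should be fixed. The omission and the missing declaration are plain from the text. The confounding of the 8 mg contrast follows from the randomization plan and needs no assumption about rates. Its size does: about 0.15 to 0.58 points for 94-day risks of 2% to 8% with half of Phase A placebo in Part 1, less if fewer are in Part 1 or bleeds come early, and zero if risk does not differ by period. It stays well inside the CI half-width. This is a modest, avoidable distortion of one important safety contrast. Confidence is high for the inconsistency; the magnitude is illustrative.

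**What to change.** In SAP 7.6.1, restore study time period (1A, 2A, 2B) as the stratum for the bleeding differences and their CIs, and name the method. A Mantel-Haenszel risk difference with a stratified CI is one option. For 8 mg this becomes the comparison with concurrent 2B placebo. For rare events such as intracranial hemorrhage, exact CIs within 2B can be used for 8 mg. Keep the crude exact proportions by arm as descriptive output. If dropping the stratum is deliberate, declare and justify it in the SAP.

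A secondary gap is that SAP 7.5.1 does not say how the CI for the relative risk reduction is computed or whether it is period-adjusted. State the method and use the adjustment already applied in the gMCP-Mod step. Only non-concurrency matters there, because the endpoint is at Day 28 in both Parts, and the primary dose-response test is already adjusted.

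The cost is SAP wording and minor programming, with no change to data collection. The 8 mg bleeding contrast loses about 6% in standard error, and an asymptotic stratified interval gives up exactness where it replaces an exact one.

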7.6.2 Deaths

All reported deaths after a subject is enrolled (i.e., has signed the informed consent) will be listed separately by subject. Deaths will also be summarized by treatment group according to whether the death was determined to be CV-related, not CV related, or unknown, following adjudication.

7.6.3 Serious Adverse Events

All reported serious adverse events (SAEs) will be listed for all enrolled subjects. A summary of SAEs occurring from the day of the first dose of study drug through 30 days following the last dose of study drug will also be provided for all treated subjects by SOC and PT for each treatment group. A separate summary of SAEs related to study drug will also be provided.

7.6.4 Adverse Events

All AEs will be summarized by SOCs and PTs for each treatment group and also listed.

Adverse events which occur on or after the first dose of study treatment and within 4 days after the last dose of study treatment will be tabulated. Events will be assigned to the study treatment administered to the subject. The proportion of subjects having an adverse event will be calculated as the number of subjects experiencing the event, divided by the total number of subjects receiving study treatment.

A high-level summary will be presented by treatment group that counts subjects experiencing any of the following:

- At least one AE
- At least one related AE

- Deaths
- At least one SAE
- SAE leading to discontinuation of study drug
- AE leading to discontinuation of study drug

The above summary will also be presented by treatment and study time period (1A, 2A, 2B), and for study part 2.

All AE listings will indicate the unique subject identifier, age, gender, current treatment, the date of onset, the date of resolution, day of onset relative to the start of treatment, action taken, investigator's assessment of severity and relationship to study drug. Additional listings will be provided for adverse events leading to discontinuation, serious adverse events, adverse events leading to death, and adverse events without a recorded resolution. Summaries of adverse events will include adverse events, adverse events by intensity, adverse events leading to discontinuation, and adverse events by relationship.

All adverse events will be further summarized according to demographic factors for each of the categories given below:

- Age category I, in years (< 65, ≥ 65)
- Age category II, in years (< 65, ≥ 65- < 75, ≥ 75)
- Gender (male, female)
- Race (White, Black or African American, Asian, American Indian or Alaska Native, Native Hawaiian or Other pacific islander, Other)

Where a subject has multiple adverse events within the level of summarization in a single analysis period, the subject will only be counted once at that level of summarization in the adverse event frequency tables.

When a subject has the same adverse event, based on preferred terminology, reported multiple times in a single analysis period, the following criteria, in order of precedence, will be used to select the event to be included in summary tables:

- Relationship to study medication
- Intensity of event

When reporting adverse events by intensity, summary tables will be provided based on the most intense event during the analysis period - independent of relationship to study medication. Similarly, where a subject has multiple adverse events within the level of summarization in a single analysis period, the subject will only be counted once at that level of summarization in the adverse event frequency tables

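### The SAP omits, without declaring it, the by-treatment summary of adverse events of special interest in Protocol 8.4.3, and it contains no grouped count of investigator-reported renal events

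*SAP*

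**What the plan says.** Protocol 8.4.3 (Safety Analyses) plans adverse event summaries for each treatment group, "including summaries of AEs, SAEs, AEs leading to discontinuation, and AEs of special interest". The phrase is not defined there or elsewhere in the protocol, and no term list is given.

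The SAP has four places where a special-interest summary could appear:

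- SAP 7.1.1, the list of tables by study period: "Adverse events, including overall AEs, SAEs, AEs leading to discontinuation, related AEs, and deaths". Its first three items match the protocol, and related events and deaths then stand where the protocol has events of special interest.
- SAP 7.6, the general safety section: "All recorded adverse events will be listed and tabulated by SOC, PT, treatment and overall".
- SAP 7.6.4, the overview table: "A high-level summary will be presented by treatment group that counts subjects experiencing any of the following". The rows are any event, any related event, deaths, any serious event, serious event leading to discontinuation, and event leading to discontinuation.
- SAP 7.6.4, the list of outputs: "Summaries of adverse events will include adverse events, adverse events by intensity, adverse events leading to discontinuation, and adverse events by relationship".

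On departures from the protocol, SAP 7.2.2 says: "Any changes from planned protocol-specified analyses will be defined in the SAP and reported in the CSR". SAP 2.4, after describing the change in top dose and randomization, says: "No further updates had a significant impact to the statistical methods planned for this study".

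**The concern.** A safety analysis named in the protocol has no counterpart in the SAP, and nothing records that it was dropped on purpose. SAP section 9 bases the statistical content of the study report on the SAP, so the summary may simply never be produced.

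The gap matters more here because of why the trial was amended. Amendment 06 lowered the top dose and held that arm closed after kidney tubular changes in a 90-day monkey study. Kidney events reported by investigators can be recorded in more than one way. Protocol 6.3 has clinically significant laboratory abnormalities reported as adverse events and prefers a clinical term only where possible, so clinical and laboratory-style terms can both occur. The SAP tabulates adverse events by organ class and preferred term ("All AEs will be summarized by SOCs and PTs for each treatment group and also listed") and has no row that brings renal terms together. A modest excess at 8 mg could be spread over several rows with few events each. A renal grouping chosen after unblinding would be open to the charge that it was picked to fit the data.

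**Working it through.** **Text comparison.** Protocol 8.4.3 names four adverse event summaries.

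| Protocol 8.4.3 | SAP 7.1.1 | SAP 7.6.4 overview |
|---|---|---|
| Any adverse event | Yes | Yes |
| Serious | Yes | Yes |
| Leading to discontinuation | Yes | Yes |
| Of special interest | No | No |

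The term does not appear in the visible SAP. Neither SAP 7.2.2 nor 2.4 declares its removal. The Amendment 06 change list for Protocol 8.4.3 does not remove it, so the requirement is in force.

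**Other renal and bleeding coverage.** SAP 7.6.5 gives, by arm, summary statistics for eGFR, the proportion above the upper limit of normal for cystatin-C, NGAL and KIM-1, and marked abnormalities, which include creatinine, BUN and urinalysis. SAP 7.6.1 analyses major plus clinically relevant non-major bleeding, all reported bleeding and intracranial hemorrhage, with differences from placebo and 95% CIs. What is left uncovered is a grouped count of investigator-reported renal events.

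**Illustration of what grouping adds.** The plan has no figure to reproduce. Inputs:

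- Planned randomized numbers from SAP Table 5-1: placebo 44 + 34 + 270 = 348, and 8 mg 270. The safety set is treated subjects, so actual numbers will be slightly lower.
- Renal event rates are assumptions, because the documents give none.
- Power is the sum, over all pairs (x, y), of Bin(x; n0, p0) × Bin(y; n1, p1) for tables with a one-sided Fisher exact p ≤ 0.025.
- One of three equal preferred terms has rates p/3. An organ-class row holding two-thirds of the events has rates 2p/3.

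| Placebo vs 8 mg | Expected events (348 / 270) | Grouped | Organ-class row, 2/3 of events | One of 3 equal terms |
|---|---|---|---|---|
| 2% vs 4% | 7.0 / 10.8 | 0.24 | 0.14 | 0.05 |
| 1% vs 3% | 3.5 / 8.1 | 0.33 | 0.19 | 0.05 |
| 2% vs 5% | 7.0 / 13.5 | 0.46 | 0.29 | 0.11 |
| 1% vs 4% | 3.5 / 10.8 | 0.60 | 0.39 | 0.12 |

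Per-row power understates what a reader of three rows would see. Treating the rows as independent, with no adjustment, the chance that at least one reaches the threshold at 1% vs 4% is 1 − (1 − 0.1245)³ = 0.33, still below 0.60.

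**Concurrent controls.** Of the 348 placebo subjects, 44 + 34 = 78 are planned before the 8 mg arm opens. Under SAP 2.2 no Phase B subject is in Part 1, so every 8 mg subject has 90-day planned treatment, while some of those 78 may have 28 days. With the 270 concurrent placebo subjects, grouped power in the four scenarios is 0.20, 0.27, 0.40 and 0.52.

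**The case against.** The strongest reply is that this is a documentation mismatch and the renal argument is added to it. Several parts of that reply stand.

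- **The renal link is inferred.** The protocol neither defines events of special interest nor names renal events among them. Restoring its phrase word for word would not produce a renal count. A reader might infer that the omission is what leaves renal events compared one term at a time. The documents do not support that, because the grouping was never specified in either document.
- **Renal safety is not neglected.** A reader might infer that a kidney signal would go unseen. SAP 7.6.5 has dedicated renal laboratory analyses from scheduled samples, and Protocol 7.1 requires DMC review of safety and laboratory data before 8 mg opens. The gap is confined to investigator-reported events.
- **How far terms would scatter is unknown.** The organ class to which a term is coded depends on a dictionary outside the documents. Protocol 6.3 also prefers clinical terms, which limits scatter.
- **Power is only a yardstick.** The protocol synopsis has safety endpoints other than bleeding summarized descriptively. At the smaller assumed differences even a grouped count would usually miss the excess.
- **Unseen sources may help.** SAP 7.6 follows a company guideline and SAP section 9 defers tables to a Data Presentation Plan. Either may hold such a table.

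The last point does not cure the omission. A table in another document is not a change defined in the SAP, which is what SAP 7.2.2 promises. Nor do laboratory summaries fully replace event reports: in the protocol's schedules Day 10 is a telephone contact, so no central chemistry is planned between discharge and Day 28, and an event between those visits reaches the database mainly through investigator reporting.

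**Conclusion.** The point holds as an undeclared inconsistency between protocol and SAP: one of the four adverse event summaries in Protocol 8.4.3 is missing from SAP 7.1.1, 7.6 and 7.6.4. Its practical weight is moderate. It rests on the judgment that renal events belong among those of special interest, which follows from the reason for Amendment 06 and not from any definition in the protocol. Under the assumed rates, a pre-specified renal group would raise the chance of noticing an excess at 8 mg by roughly 1.5 to 1.7 times over an organ-class row holding two-thirds of the events, and by about 4 to 6 times over a single one of three equal terms. Other rates or other splits would change those ratios. No efficacy conclusion, sample size or error rate is affected.

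**What to change.** Before unblinding, add an adverse-events-of-special-interest row to the SAP 7.6.4 overview and to the SAP 7.1.1 by-period list. Define it by one fixed renal term list covering both clinical renal terms and laboratory-style renal terms reported as adverse events. Report subjects with at least one such event by treatment and study period, with the difference from placebo and a descriptive 95% CI. Compare 8 mg with placebo subjects randomized in Phase B. A separate bleeding group is not needed, because SAP 7.6.1 already provides it. The interval goes beyond Protocol 8.4.3, which plans differences with CIs for bleeding endpoints only, so label it descriptive.

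If the sponsor prefers not to produce the summary, declare and justify the removal in the SAP, as SAP 7.2.2 requires.

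The cost is a term list and one or two tables from data already collected. Restoring the summary needs no protocol amendment, because the protocol already plans it.
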